#### Missed visits due to the COVID-19 pandemic

Missed visits will be attributed to the COVID-19 pandemic if the eCRF comments log for the missed visit contains a COVID-19 reference.

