The categories for assigning reasons in the eCRF are: 'lack of efficacy', 'AE', 'withdrawal by subject', 'lost to follow-up', 'death', or 'other'. If 'AE' or 'other' is selected, a specification must be provided in the eCRF.

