14.1 Sample size

With a significance level of 5%, a sample size of 250 subjects will provide 99% power for detecting a treatment difference for the primary endpoint, assuming an EASI75 response rate at Week 16 of 40% vs 15% for tralokinumab+TCS and placebo+TCS, respectively. Assuming a response rate of 30% vs 15% in reduction of Worst Daily Pruritus NRS (weekly average) score of at least 4 from baseline to Week 16 for tralokinumab+TCS and placebo+TCS, respectively, the trial will provide at least 80% power for rejecting the hypotheses related to the primary endpoint and the secondary endpoint evaluating pruritus at Week 16.

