14.3.16 General principles

Unless otherwise stated, all significance tests will be 2-sided using the 5% significance level. All CIs will be presented with 95% degree of confidence. An observed-cases approach will be used for tabulations of data by visit (i.e. involving only those subjects who attended each specific visit).

Categorical data will be summarised using the number and percentage of subjects in each category and treatment group. Continuous data will be summarised using the mean, median, standard deviation, 1st quartile, 3rd quartile, minimum, and maximum values.

All the analyses specified in the protocol will be reviewed in relation to the blinded data actually obtained and the statistical analysis plan and the analysis set definition document will be finalised before breaking the randomisation code.

Any changes from the statistical analysis planned in this clinical trial protocol will be described and justified in a protocol amendment, the statistical analysis plan, and/or in the CTR dependent on the type of deviation.

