Appendix 8: Clinical Trial Protocol Addendum COVID-19

1 Rationale for clinical trial protocol addendum

The current COVID-19 pandemic warrants many subjects in the ECZTRA 7 trial to stay at home to comply with authority issued preventive measures. This make visits to the sites challenging, and in some cases impossible. To follow authorities restrictions and to safeguard the subjects in ECZTRA 7 as well as providing continued therapy to secure the scientific integrity, this clinical trial protocol addendum is installed to provide an opportunity for subjects to continue treatment with tralokinumab via home-use (self-injection).

No safety issues have been observed in subjects who applied home-use of IMP after training by site staff in previous or ongoing clinical trials with tralokinumab. Therefore, no safety issues are expected regarding home-use of IMP in ECZTRA 7.

2 GCP statement

Normal GCP procedures are followed for this protocol addendum. Subjects will be verbally informed and verbally consent to providing contact details (name, address, and telephone number) for shipping purposes.

3 eCRF recording

It must be recorded in the eCRF if the visit was conducted as a home-visit.

If the subject is reached by telephone/video contact and collection of AEs, concomitant medication and pregnancy test result (if applicable) are assessed, "Visit date" must be documented in the eCRF. All other assessments should be marked "Not done". The log line "If not done, specify reason" must be answered with "COVID-19". In addition, in the "Comments log", one log line per visit should be entered with "COVID-19" – as reason for only partly performed assessments at the visit.

If no contact can be established between site and subject at a given visit, this must be recorded as a missed visit in the eCRF ("Not done"). The log line "If not done, specify reason" must be answered with "COVID-19".

4 Description of visit scenarios

Without compromising the safety of subjects and site personnel, it is expected that efforts are made to secure attendance at sites for the Week 16 and Week 26 visits, securing important efficacy and safety assessments for the trial. Dependant on national guidelines regarding

COVID-19 and subject preferences, the remaining visits can follow three different scenarios as described below:

- 1) The subject is not restricted from attending visits at the clinic and continue to follow all procedures specified in the protocol.

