5.2 Injections of tralokinumab

Prior to self-injection at home, the subject will receive proper training in SC injection technique and on procedures to be followed in case of an emergency during or following home-use of tralokinumab. Tralokinumab will be injected by the subject when AE assessments have been completed.

All IMP self-injections need to be documented in the eCRF with 'COVID-19' written in the comments log for the visit in scope.

Subjects who misses one or more doses need to be documented in the eCRF with 'COVID-19' written in the comments log for each visit in scope.

Further details on IMP-injection are provided in the Trial Product Handling Manual. Subjects will also receive a pamphlet with instructions for IMP home-use and a Log of Drug Administration.

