#### Permanent discontinuation of IMP due to the COVID-19 pandemic

Permanent discontinuation of IMP will be attributed to the COVID-19 pandemic if reason for permanent discontinuation of IMP contains a COVID-19 reference.

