#### Missed IMP doses due to the COVID-19 pandemic

Missed IMP doses can be attributed to the COVID-19 pandemic if one of the following occurs:

1. Missed visit due to the COVID-19 pandemic, implying that IMP dosing at that scheduled visit then also is missed due to the COVID-19 pandemic.
2. The eCRF comments field for the administration of IMP contains a COVID-19 reference.

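### A pandemic-missed, no-contact Week 26 visit recorded exactly as sites were told can be scored as non-response, because the SAP searches a different eCRF field; missed doses have a similar gap

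*SAP*

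**What the plan says.** **Missed visits.** SAP 6.8.8: "Missed visits will be attributed to the COVID-19 pandemic if the eCRF comments log for the missed visit contains a COVID-19 reference". The rules for missing assessment data in the same section build on this. An assessment is attributed if its visit is attributed, if the visit was held by telephone or video with a reference in the comment log, or if the comments field for the missing assessment has a reference.

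Protocol Appendix 8, Section 3 separates two cases. If the subject is reached by telephone or video, undone assessments get COVID-19 in the line *If not done, specify reason*, and the comments log gets an entry for that visit as well. If no contact is made, "this must be recorded as a missed visit in the eCRF" and the same reason line is completed. No comments-log entry is requested in that paragraph.

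**Missed doses.** SAP 6.8.8 attributes a missed dose either through a missed visit that is itself attributed, or if "The eCRF comments field for the administration of IMP contains a COVID-19 reference". Appendix 8, Section 5.2 says "Subjects who misses one or more doses need to be documented in the eCRF" and puts the COVID-19 entry in the comments log of each visit concerned.

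**What attribution decides.** Under Protocol 14.3.8.1 and Panel 13, a binary value missing before any intercurrent event is multiply imputed if it is missing because of the pandemic, and is non-response otherwise.

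**The concern.** Attribution is the switch between imputation and failure in the primary binary estimand. Protocol 14.3.1 itself doubts that non-response is reasonable for data lost to the pandemic. The search rule therefore has to cover the field in which sites were told to write. For one type of visit it does not clearly do so, and the endpoints exposed, EASI75 and IGA 0/1 at Week 26, are secondary endpoints in the testing hierarchy of Protocol 14.3.6. For missed doses the stake is indirect. An unattributed missed dose can turn pandemic-related rescue into ordinary rescue, which is non-response, or can leave a prolonged interruption undetected.

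**Working it through.** **Instructions and search rules side by side**

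| Situation | Where sites are told to write COVID-19 | Where SAP 6.8.8 looks | Found? |
|---|---|---|---|
| No contact, visit with a dose due (includes Week 16) | Reason line; also comments log, through the missed-dose instruction | Comments log | Yes, if sites apply Appendix 8, 5.2 |
| No contact, Week 26 | Reason line only | Comments log; for assessments also their comments field | Not unless the reason line counts as a comments field |
| Telephone or video visit, any week | Reason line and comments log | Comment log | Yes |
| Dose missed at a conducted or telephone visit | Visit's comments log | IMP administration comments field | Not as worded |

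Week 26 stands alone because the last dose is at Week 24 (Protocol 7.1 and 9.2.1), so the missed-dose entry never arises there.

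**Missed dose, followed through.** Protocol 14.3.1 attributes rescue to the pandemic in three windows. The first opens at a conducted visit where the dose was not given because of the pandemic, so it depends on the IMP-field rule. If that rule misses the entry, rescue in the window becomes ordinary rescue, including before Week 16. Prolonged interruption needs only one attributed event in the run. It is lost only if every missed dose in the run, and any missed visit that counts towards it, goes unattributed.

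**The plan's own figure.** Inputs from Protocol 14.1: "a sample size of 250 subjects will provide 99% power", at 40% against 15%. Allocation is 1:1, so 125 per arm. Protocol 14.3.16: "all significance tests will be 2-sided using the 5% significance level".
- Pooled rate 0.275; null SE = √(2 × 0.275 × 0.725/125) = 0.0565.
- Alternative SE = √((0.40 × 0.60 + 0.15 × 0.85)/125) = 0.0542.
- z = (0.25 − 1.96 × 0.0565)/0.0542 = 2.57, so power is 0.995. The stated 99% reproduces.

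**Size per subject.** Assume that imputation would have given a subject the arm's response probability p. Setting the value to non-response lowers the arm's expected rate by p/125. The protocol gives no Week 26 rates, so the Week 16 planning rates for EASI75 are borrowed.
- Tralokinumab: 0.40/125 = 0.32 percentage points.
- Placebo: 0.15/125 = 0.12 percentage points.
- One subject in each arm: the difference falls by 0.32 − 0.12 = 0.20 points.

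**Illustrative range.** The documents support no particular share. If a share k of each arm were affected, the difference would be 25 × (1 − k) points:

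| k (assumed) | Subjects per arm | Difference | Power |
|---|---|---|---|
| 0 | 0 | 25.0 | 0.995 |
| 2% | 2.5 | 24.5 | 0.994 |
| 5% | 6.25 | 23.75 | 0.992 |
| 10% | 12.5 | 22.5 | 0.987 |

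With unequal shares a (tralokinumab) and b (placebo), the difference is 0.40(1 − a) − 0.15(1 − b). It exceeds 25 points only if b > (0.40/0.15)a = 2.67a. For example, a = 5% and b = 15% gives 0.380 − 0.1275 = 25.25 points; a = 10% and b = 5% gives 0.360 − 0.1425 = 21.75 points.

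**The case against.** The best defence is that the SAP can be read more widely. Its paragraph on search terms speaks of any comment fields or logs, and the third condition for missing assessments uses the comments field of the assessment itself. If the not-done reason line is such a field, the Week 26 efficacy gap closes. That depends on an eCRF layout the documents do not show. The wider phrase introduces alternative search words, while the missed-visit and missed-dose rules each name a specific field. The defence shows that misclassification is possible, not certain.

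The affected group is also narrow. The subject must be out of reach even by telephone at Week 26, although Appendix 8 asks sites to secure that visit and Appendix 9 adds contact with subjects who cannot attend. This stands.

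On doses, Protocol 9.8.4 requires the reason for any non-compliance with IMP administration to be recorded in the eCRF, so the IMP field may often hold the reference as well. A missed dose is also not itself a failure under Panel 13. Both points stand and limit the second gap without removing it.

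A reader might infer that pandemic-driven withdrawals suffer the same field mismatch. The documents do not support that. The SAP rule is "Permanent discontinuation of IMP will be attributed to the COVID-19 pandemic if reason for permanent discontinuation of IMP contains a COVID-19 reference", and the reason is the field that Protocol 10.3 and 11.8 require. Protocol 14.3.1 adds that the causal link will be documented in the eCRF. Text is mandatory only when an adverse event or the residual category "is selected, a specification must be provided in the eCRF", so a stop coded otherwise may carry no reference. That is a possible coding weakness, not a search in the wrong place.

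**Conclusion.** The point holds in limited form. Read literally, the recording instruction and the search rule do not meet for a no-contact Week 26 visit, so EASI75 and IGA 0/1 at Week 26 can be scored as non-response where the estimand intends imputation. They also do not meet for a dose missed at a conducted or telephone visit, which matters only through rescue attribution or prolonged interruption.

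The effect is about 0.32 points (tralokinumab) or 0.12 points (placebo) of expected EASI75 rate per misclassified subject. This rests on 125 per arm, borrowed Week 16 rates and imputation at the arm's average. The number of subjects is unknown and probably small. With equal shares in both arms the difference shrinks, so the error is conservative.

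Two stronger inferences are not supported. One is that subjects are in fact being miscounted on a material scale: no document gives a count. The other is that the missed-visit gap threatens the Week 16 primary endpoint: a dose is due at Week 16, so the missed-dose instruction covers it. Only the missed-dose route can reach Week 16. The missed-visit gap also leaves the primary, hypothetical analysis of SCORAD and DLQI untouched, because a missing Week 26 value there is handled the same way whatever its cause.

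**What to change.** Before unblinding, amend SAP 6.8.8 in two places.

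1. Missed visits and missing assessment data: search the line *If not done, specify reason* as well as the comments log.
2. Missed IMP doses: where a dose was not given, also use the visit's comments log. Add blinded review, so that a dose missed for another recorded reason, such as an adverse event, is not attributed to the pandemic. The review is needed because Appendix 8 puts COVID-19 in that log for every telephone or video visit and every self-injection.

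Leave the discontinuation rule as it is. Reclassifying withdrawals from the comments logs of their last visits would, for the same reason, label ordinary home-use subjects as pandemic withdrawals and move real failures into imputation.

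The cost is a small programming change on data already collected, some blinded review, and a few more values imputed instead of set to non-response. No estimand changes.

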#### Missed IMP doses due to the COVID-19 pandemic

Missed IMP doses can be attributed to the COVID-19 pandemic if one of the following occurs:

1. Missed visit due to the COVID-19 pandemic, implying that IMP dosing at that scheduled visit then also is missed due to the COVID-19 pandemic.
2. The eCRF comments field for the administration of IMP contains a COVID-19 reference.

#### Use of rescue treatment due to unavailability of IMP related to the COVID-19 pandemic

As stated in the protocol, attributing rescue treatment to the COVID-19 pandemic depends on either missed IMP dosing, missed visits or permanent discontinuation of IMP, due to the COVID-19 pandemic and thus the definition depends on the previous defined events.

#### Prolonged interruption of IMP due to the COVID-19 pandemic

As defined in the protocol and using the defined methods for missed IMP doses due to the COVID-19 pandemic and missed visits due to the COVID-19 pandemic.

#### Missing assessment data due to the COVID-19 pandemic

Assessment data missing will be attributed to the COVID-19 pandemic if one of the following occurs:

1. The visit where the assessment is scheduled to occur is missed due to the COVID-19 pandemic.
2. The visit where the assessment was scheduled to occur is not missing but is indicated to have been a telephone/video visit by having a COVID-19 reference in eCRF comment log implying that the assessment was not possible to do.
3. The eCRF comments field for the missing assessment data contains a COVID-19 reference.

### 6.8.9 Treatment labels

**Table 10: Treatment labels for the clinical trial report text and tables**

Period	Label Used in Text	Label Used in Tables	Order in Table
Treatment period	Tralokinumab Q2W + TCS	Tralokinumab Q2W + TCS	1
Treatment period	Placebo + TCS	Placebo + TCS	2

